13.2.2. Pharmacokinetic Endpoints

Dose linearity for the pharmacokinetic parameters AUC and C_{\max} will be tested using a standard power model such as, $AUC = \alpha + \text{dose}^{\beta}$, which is equivalent to $\log(AUC) = \log(\alpha) + \beta \cdot \log(\text{dose})$. Linearity (also called dose proportionality) will be accepted if β is not significantly different from 1 at a nominal 10% level of significance.

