[name]
 Mayo Clinic
 Division of Hematology
 Dept. of Internal Medicine
 [name]
 [name]
 [contact]
 [contact]
 [contact]

IND Sponsor Contact Information:

[name].,
 IGF Oncology,
 [name],
 [name]
 [contact]
 [contact]

Synopsis

Primary Objective:

The primary objective of this study is to determine the safety and tolerability of utilizing the insulin-like growth factor-1-methotrexate conjugate, 765IGF-MTX for the treatment of advanced, previously treated myelodysplastic syndrome (MDS), chronic myelomonocytic leukemia (CMML) and oligoblastic acute myelogenous leukemia (oligoblastic AML or O-AML), including determining the maximum tolerated dose (MTD).

Secondary Objective:

The secondary objective of this study is to determine the clinical benefit of 765IGF-MTX as measured by partial and complete remission rates, relapse-free survival, and overall survival in patients with advanced, previously treated MDS, CMML, or O-AML.

Patient Population:

[figure not shown]
- Diagnosis of MDS, CMML or O-AML that is refractory to or intolerant of standard therapy and is no longer likely to respond to such therapy
- Patient must have recovered from the acute toxic effects (\leq grade 1 CTCAE v.4.0) of previous anti-cancer treatment prior to study enrollment
- Age 18 years or older
- ECOG performance status 0, 1, or 2 (appendix III)

Study Design:

This pilot study will evaluate use of IGF-Methotrexate conjugate (765IGF-MTX) in patients with advanced, previously treated MDS, CMML and O-AML. 765IGF-MTX at a dose of 0.20 to 2.5 μ equivalents per kg is administered as an IV infusion over 1.5 hours on days 1, 8 and 15 of a 28 day cycle. Treatment continues until disease progression, as assessed after 2 cycles, unacceptable toxicity, or patient refusal. Assessment of response will be confirmed by bone marrow studies performed at the end of cycles 2, 4, and 6 (each +/- 3 days).

Once a final maximum tolerated dose level (MTD) is determined, the pharmacokinetics (PK) of 765IGF-MTX will be assessed on days 1 and 2 and days 15 and 16 of cycle 1 at the MTD in three patients.

Study Schema

Pharmacodynamic samples on day 1 of cycle 1, days 1 and 15 of cycle 2, and day 15 of cycles 4 and 6 before 765IGF-MTX administration.

At the MTD: Pharmacokinetic samples starting on day 1 (including time points on day 2), and day 15 (including time points on day 16) of cycle 1

Dose Finding Component: 1 cycle = 28 days

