8.2. Research Related Procedures

	Baseline (within 28 days of Cycle 1, D1)	C1D1	C1 D15	C2 D1	C2 D15	Every 8 weeks (± 1 week) up to week 24	Cycles 4 and 6, D15
PKs per section 9.1		x ¹	x ¹				
ECG (QT study) done during PK blood collection per section 9.3. PK patients only. ²		x ²	x ²				
Serum IGF-1 level. All subjects.		x ³		x ³	x ³		
Plasma and whole blood IGF-1R level. All subjects.		x ³		x ³	x ³		x ³
Anti-765IGF antibody assay. All subjects.		x ³		x ³	x ³		x ³
Neutralizing antibodies. All subjects.		x ³		x ³	x ³		x ³
IGF-1R expression in bone marrow biopsy and aspirate by IHC and flow cytometry. All subjects.	x ⁴					x ⁴	
IGF-1R expression in blood cells by flow cytometry. All subjects.	x ⁵					x ⁵	

¹ Done only in the PK patients in the MTD. Pre-765IGF-MTX infusion (at the time of am labs if am labs are within one hour of 765IGF-MTX infusion), 5 min before the infusion ends (+/- 5 minutes), and at the following time points after completion of the infusion: 30 min (+/- 5 minutes), 60 min (+/- 15 minutes), 2 h (+/- 15 minutes), 4 h (+/- 15 minutes), 6 h (+/- 15 minutes), 8 h (+/- 15 minutes and 24 h (+/- 2 hours)). The 8 hour time point will be collected on day 1 but not on day 15.

² Done only in PK patients in the MTD. Pre-765IGF-MTX infusion (+/- 5 minutes), and 30 min (+/- 5 minutes) after starting the infusion, at the following time points after completion of the infusion: 60 min (+/- 15 minutes) and 3 hours (+/- 15 minutes). In all patients, ECG is done at baseline, on day 1, cycle 1 (before the infusion), and 30 days (± 1 week) after the final dose (see section 8.1).

³ Blood draw prior to infusion

⁴ Bone marrow biopsy and aspirate will be collected at baseline and every 8 weeks (± 1 week) up to week 24, i.e., after cycles 2, 4, and 6, before the first dose of the next cycle. If no bone marrow aspirate viably frozen for flow cytometry is available from a patient in the 28-day baseline period before cycle 1, day 1, the patient may still enroll and no new bone marrow biopsy will be required for a baseline sample.

⁵ Whole blood collection in EDTA tubes.

9. Correlative Studies

Information on the collection of blood samples for the correlative studies (collection tubes to be used, volume of blood drawn, collection processing, aliquot procedure and storage, and particular assay to be used) can be found in a laboratory manual to be supplied.

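### Section 13.2.2 accepts dose proportionality when a test fails to reject, so thin or noisy PK data favour a finding of linearity; at the one dose level planned for PK, the exponent cannot be estimated

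*Combined protocol and SAP*

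**What the plan says.** Section 13.2.2 says that dose linearity of AUC and Cmax "will be tested using a standard power model such as" the one it prints, with exponent beta on dose. The decision rule follows: "Linearity (also called dose proportionality) will be accepted if" beta "is not significantly different from 1 at a nominal 10% level of significance". The section gives no equivalence margin, no confidence-interval criterion for beta, and no minimum number of patients or dose levels.

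No other section fills the gap. Sections 9.1.4 and 13.5.1 list descriptive PK statistics. Section 13.2 promises confidence intervals for means, medians, percentages and the antibody correlations, but not for a regression slope. Section 13.1 says that inferential testing does not determine the sample size.

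The Synopsis and the dose-level table give five levels: 0.20, 0.40, 0.80, 1.6 and 2.5 µEq/kg. PK sampling is narrower. Footnote 1 in section 8.2 reads "Done only in the PK patients in the MTD"; the Synopsis says three patients, and section 4 says at least three of the nine at the MTD. Section 9.1.1 places the sampling on days 1 and 15 of cycle 1. Section 4 allows intra-patient escalation only after two cycles, so it adds no second dose level to those data.

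**The concern.** A non-significant test of beta = 1 shows only that the data did not exclude 1. Fewer patients, a narrower dose range or more variability widen the uncertainty in beta and make non-rejection more likely. The rule therefore rewards weak data: an uninformative study has close to a 90% chance of being called linear, the same chance as a study in which PK really is proportional. Testing at 10% instead of 5% softens this but does not remove it.

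At stake is the reported PK conclusion. A statement that proportionality was accepted would read as a positive finding when the data may be compatible with clearly non-proportional exposure.

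**Working it through.** The documents give no power, margin or variability for this test, so there is no planned figure to reproduce. The check asks how often the stated rule accepts proportionality when it is false.

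**Inputs from the documents.** The five dose levels; the 10% level (sidedness is not stated, and a difference in either direction is read as two-sided); the log-log form of the model.

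**Assumptions not in the documents.** Between-patient CV of AUC of 40%, range 30–60%; the true beta; the number of PK patients per level where PK is imagined beyond the MTD; a log-SD of body weight of 0.2.

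**Method.** Regress log(AUC) on log(dose). Then sigma = sqrt(ln(1 + CV²)) and SE(beta) = sigma / sqrt(Sxx). The rule accepts when |beta-hat − 1| / SE-hat is below the 95th percentile of t with n − 2 df. The probability of this comes from the noncentral t with noncentrality (beta − 1)/SE. At beta = 1 it is 90% for any design.

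**1. Hypothetical PK at all five levels, 1, 1, 1, 3 and 3 patients (n = 9).**
- ln(dose): −1.609, −0.916, −0.223, 0.470 (three times), 0.916 (three times); mean 0.157.
- Sxx = 3.119 + 1.151 + 0.144 + 0.294 + 1.731 ≈ 6.44.
- True beta 1.3: AUC departs from proportionality by 12.5^0.3 = 2.13-fold over the range 2.5/0.20 = 12.5.
- Critical t (7 df) = 1.895.

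| CV | sigma | SE(beta) | noncentrality | P(accepted) |
|---|---|---|---|---|
| 30% | 0.294 | 0.116 | 2.59 | 25% |
| 40% | 0.385 | 0.152 | 1.98 | 45% |
| 60% | 0.555 | 0.219 | 1.37 | 66% |

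**2. Less information, more acceptance.** Again for a true beta of 1.3 over five levels, three patients per level (n = 15) give acceptance in 4% of trials at CV 30% and 32% at CV 50%. One patient per level (n = 5) gives 51% and 73%.

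**3. PK as planned, at the MTD only.** On the µEq/kg scale every PK patient has the same log(dose), so Sxx = 0 and beta is not estimable. If absolute dose were used instead, log(dose) would vary only with body weight. Averaging over simulated weights with log-SD 0.2, a true beta of 0.5 (or, by symmetry, 1.5) would be accepted about 89–90% of the time with 3 patients and about 77–86% with 9, for CVs of 30–60%. With three patients the rule barely separates half-power or 1.5-power PK from proportional PK.

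**4. The printed equation.** The text shows alpha added to dose^beta and calls this equivalent to the log-log line. The log-log line requires alpha multiplied by dose^beta. With alpha = 10 and beta = 1, the additive form runs from 10.2 to 12.5 over the five doses and the multiplicative form from 2 to 25, so the two are not equivalent.

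**The case against.** The strongest reply is that the rule cannot do harm as the trial is planned: with PK at one dose level there is no slope to test, so nothing can be wrongly accepted on the per-kg scale. That is right, and it makes the five-level figures conditional on a design the documents do not contain. It does not rescue the rule. Section 13.2.2 still commits to the test, and adding PK at other levels, or switching to absolute dose, would bring the rule into use.

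It can also be said that PK is correlative, that it is otherwise summarised descriptively, and that section 13 is an overview with a full SAP to follow before database lock. All of this stands and limits the importance of the point. The later SAP could add a margin, but the acceptance rule is already stated.

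Four stronger readings are tempting and not supported:
- *Any data would be accepted as linear.* False. With three patients at each of five levels and a CV of 30%, a true beta of 1.3 is accepted in only 4% of trials.
- *Two adjacent doses give the clearest example.* With 3 + 3 patients at doses 2-fold apart and a CV of 40%, a true beta of 1.5 is accepted 76% of the time (67–83% for CVs of 30–60%). But over a 2-fold dose range that is only a 2^0.5 = 1.41-fold departure. A 2-fold tolerance would allow beta from 0 to 2, so this acceptance need not be an error.
- *The wrong model will be fitted.* The plus sign may be a slip or come from reading the PDF, and the log-log form beside it makes the intention clear.
- *The result will set doses or the MTD.* Section 4 bases the MTD on DLTs, and no section says that a proportionality result determines later dosing.

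**Conclusion.** The point holds as a defect in the decision rule: section 13.2.2 turns non-rejection into acceptance, and nothing elsewhere supplies a margin or an interval for beta. The 45% figure (25–66%) rests on the assumed CV, the hypothetical patient layout and a true beta of 1.3, and it illustrates the rule's behaviour without forecasting this trial. Under the sampling actually planned, the firm conclusion is that beta cannot be estimated on the µEq/kg dose; the absolute-dose figures depend on the assumed spread of body weight. The correction is worth making because it costs little, but its reach ends at a correlative PK endpoint. The printed plus sign is a minor item to check against the original document.

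**What to change.** Delete the sentence that accepts linearity when beta does not differ significantly from 1. Replace it with three statements:

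- If PK data exist at two or more dose levels, regress log(AUC) and log(Cmax) on log(dose) and report beta with its 90% CI.
- Claim proportionality only if that CI lies wholly inside an interval the sponsor fixes in advance for the dose range actually sampled; otherwise report the result as inconclusive. The width is the sponsor's choice. As an illustration, a 2-fold tolerance over the full range gives 1 ± ln 2/ln 12.5 = 1 ± 0.27, or 0.73 to 1.27.
- If PK data exist at one dose level only, state that dose proportionality is not assessed.

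Also check the printed equation and show it as AUC = alpha × dose^beta.

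The change needs no extra patients, samples or visits. The downside is that the result will usually be inconclusive. With the illustrative interval and 1, 1, 1, 3 and 3 patients, truly proportional PK would be shown in about 41%, 14% and 2% of trials at CVs of 30%, 40% and 60%. With numbers this small, that is the accurate thing to report.

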13.2.3. Safety Endpoints

Incidence rates of treatment-emergent adverse events will be summarized within treatment group at the MedDRA preferred term and primary system organ class levels. Similar summaries will be made for subsets of AEs such as (1) those judged by the Investigator to be related to study treatment, and (2) serious adverse events (SAEs). Other routine safety assessments (e.g., clinical laboratory parameters, ECG parameters, and vital signs) will be summarized by standard deviation, median, minimum and maximum observed values and changes from baseline values. NCI-CTCAE severity grades for laboratory parameters and other endpoints measured on an ordinal categorical scale may be summarized using shift tables (a two-way frequency table pairing baseline value with the most extreme post-baseline result).

Additional exploratory analyses may be performed to assist the sponsor in planning future studies.

13.3. Analysis plan for primary objective:

The primary objective is to determine safety and tolerability of 765IGF-MTX by evaluation of toxicity for the treatment of advanced, previously treated hematologic malignancies. Preliminary information will be collected for treatment related toxicity and tolerance. Toxicity will be graded using the NCI's Common Terminology Criteria for Adverse Events version 4 (CTCAE v.4.0). Treatment tolerance will be based on the number of dose-limiting toxicities, treatment delays and dose reductions. Information will be presented in a tabular and descriptive manner.

13.4 Analysis plan for secondary objectives:

13.4.1 Objective Response Rate, Relapse-Free Survival, Overall Survival and Cumulative Incidence of Relapse; descriptive statistics will be used to describe clinical benefit measured by the above parameters.

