3.3.4 Plasma 765IGF Level and 765IGF-MTX toxicity/response

3.3.5 Plasma and whole blood IGF-1R level and 765IGF-MTX Toxicity/Response

3.3.6 Assess formation of antibodies against 765IGF-MTX

3.3.7 Assess formation of neutralizing antibodies

3.3.8 IGF-1R expression level in diseased tissue in bone marrow, as measured by IHC, and flow cytometry, and in blood cells as measured by flow cytometry.

4. Overall Design and Study Plan

This pilot study will evaluate the safety and clinical benefit of 765IGF-MTX in patients with advanced, previously treated MDS, CMML or O-AML. 765IGF-MTX is administered as an IV infusion over 1.5 hours on days 1, 8 and 15 of a 28 day cycle. Treatment continues until disease progression, unacceptable toxicity, or patient refusal. Assessment of response will be confirmed with bone marrow studies performed at the end of cycle 2, and every 8 weeks +/- 7 days (2 cycles) thereafter up to the end of cycle 6, and at physician's discretion thereafter.

- Dose Finding Component: Up to 5 dose levels will be tested (refer to schema on page 6). The maximum tolerated dose (MTD) will be determined using the modified toxicity probability interval design with dose limiting toxicity (DLT) estimated at 0.33.

Our modification involves using cohorts of size 1 for the initial doses, which allows rapid escalation through the initial dose levels, and expanding to cohorts of size 3 once any grade 2 or higher toxicity is observed that is considered related to study drug (with the exception of alopecia, nausea, or diarrhea). Additional patient cohorts will not be enrolled until 1 of 1 (with no grade 2 toxicity), 3 of 3, 5 of 6, or 7 of 9 patients at the current dose level complete all planned treatment for cycle 1 (defined as 3 doses of 765IGF-MTX without DLT and are able to start cycle 2 with no more than a 2 week delay. At the discretion of the principal investigator, intra-patient dose escalation between cycles is also allowed but only after 2 cycles at one dose level and confirmation of safety in at least 3 patients treated at the higher dose level.

If none of the dose levels are acceptable at study completion, an optimal dose level will not be identified and the drug does not warrant further investigation.

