7.1. Study Drug Administration

After Cycle #1 a new treatment cycle will be initiated when all of the following conditions are met:

- Non-hematologic treatment related toxicities have improved to grade 1 or resolved (CTCAE v.4.0)
- Platelets $> 10 \times 10^9/L$

Refer to section 7.3 for guidelines for dose modifications based on treatment-related delays and toxicities of the previous cycle.

7.1.1. 765IGF-Methotrexate Administration

765IGF-MTX will be given at the assigned dose as a 1.5 hour IV infusion in 250 ml of 5% dextrose on days 1, 8, and 15 of a four-week treatment cycle. Every 4 week period will be considered one treatment cycle. Subsequent cycles must meet the criteria found in section 7.3.1 and may begin 1 day earlier to accommodate scheduling issues, or up to 4 weeks later if a patient needs this time to recover to meet criteria for start of a new cycle as specified in section 7.2.1. At the investigator's discretion, the study drug may be administered in 10% dextrose rather than 5% dextrose if it is believed necessary to prevent or control hypoglycemia.

Pre-medication

None is required, but can be utilized per clinician discretion. The program of predication below has been used in the prior solid tumor phase I with some of the later enrolled patients to prevent nausea and an allergic reaction. Nausea during infusion was seen in a few patients and a possible allergic reaction to the drug was seen in one patient.

Zofran 8mg PO
Benadryl 50mg PO
Tylenol 650mg PO
Hydrocortisone 100mg IV push
D5 .45 normal saline 100cc/hr to start with premeds

Monitoring

Vital signs including blood pressure, pulse, temperature, respirations, and pulse oximetry, and blood glucose will be measured immediately before the infusion and immediately after completion of the infusion in all patients during all cycles. IGF-MTX causes hypoglycemia at higher dose levels, so it is important to monitor blood glucose levels. During the first 28-day cycle, patients will be monitored for blood glucose on infusion days for a total of 3.5 hours. Vital signs listed above will be monitored per the following table:

Monitoring interval	
Immediately before infusion	All vitals
To Hour 1.5 (during infusion)	Glucose only, every 15 min
Hour 1.5	All vitals
Hours 1.5-3.5	Glucose only, every 30 min

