7.11. Follow-up

Administration of study medication will be continued after cycle 2 until disease progression, unacceptable toxicity, or patient withdrawal. A final study visit will occur 30 days (+/-1 week) after the last dose of 765IGF-MTX. This visit will end study participation unless there is ongoing toxicity at least possibly related to study treatment. In this case, the patient will be followed as medically appropriate until resolution or stabilization of the adverse event.

8. Study Parameters

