11.2. Adverse Event Documentation

Adverse events occurring from the first dose of 765IGF-MTX up to and including 30 days after administration of the last dose must be documented. Adverse events attributed to a study-related procedure which occur prior to the initiation of study treatment must be documented as well.

For the purposes of this study, adverse event documentation requirements will be determined based on grade, expectedness and relationship to study therapy as follows:

	Grade 1	Grade 2		Grade 3		Grade 4 and 5
	Expected or Unexpected	Expected	Un-expected	Expected	Un-expected	Expected or Unexpected
Unrelated	Not required	Not required	Not required	Not required	Required	Required

Possible						
Probable						
Definite	Not required	Required	Required	Required	Required	Required

All patients will be monitored with appropriate event documentation in EDC Easy® through the final study visit per section 7 as it is expected that most treatment related adverse events will occur during this period.

However, all toxicities (grades 1, 2, 3, 4, 5) must be reported within internal study forms, and include the following descriptors:

- Toxicity
- Grade
- Date
- Expected or Unexpected
- Attribution (unrelated, unlikely, possible, probably, definite)

For grade 2 or higher toxicities, principal investigator and/or treating physician will be notified the same day as study visit.

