13.2. Statistical Methods

Statistical analyses will be performed using SAS software version 9.4 or higher. In general, data summaries will be compiled by 765IGF-MTX dose level and overall and will include the mean,

standard deviation, median, minimum and maximum values for continuous data; the median, 25th and 75th percentiles, minimum and maximum values for time-to-event endpoints; and the number and percentage of patients in each category for categorical data. Pointwise 95% confidence intervals (CI) will also be estimated for the mean (continuous data), median (time-to-event endpoints) or percentage of patients (categorical data).

Baseline value of a characteristic is defined as the last measured value prior to the first dose of 765IGF-MTX.

Descriptive statistics such as Spearman or Pearson correlation coefficients will be estimated with 95% CIs to assess the relationship between anti-765IGF antibody and anti-765IGF-MTX antibody levels with clinical response and toxicity.

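### By-dose adverse event percentages are taken over windows of unequal length, so they mix toxicity with time at risk; a cycle 1 table and exposure figures would separate the two

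*Combined protocol and SAP*

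**What the plan says.** Section 3.1 makes safety and tolerability, assessed through AEs, the primary endpoint. Section 13.2.3 sets out the tables: "Incidence rates of treatment-emergent adverse events will be summarized within treatment group at the MedDRA preferred term and primary system organ class levels". The same layout is planned for treatment-related and serious events. Section 13.2 gives the grouping, "data summaries will be compiled by 765IGF-MTX dose level and overall", and the scale, "the number and percentage of patients in each category for categorical data". Laboratory grades may also go into shift tables "pairing baseline value with the most extreme post-baseline result"; these are optional.

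Section 13 does not define treatment-emergent. The nearest rule is in section 11.2: "Adverse events occurring from the first dose of 765IGF-MTX up to and including 30 days after administration of the last dose must be documented". On duration, section 7.11 says: "Administration of study medication will be continued after cycle 2 until disease progression, unacceptable toxicity, or patient withdrawal". No maximum number of cycles is given. Doses fall "on days 1, 8, and 15 of a four-week treatment cycle" (section 7.1.1), although the Study Schema leaves the day 8 and day 15 visits to the physician from cycle 3 on.

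Section 13 plans no cycle 1 or per-cycle AE table, no exposure summary and no rate per unit of time. Section 4, by contrast, counts DLTs in cycle 1 only, and section 13.3 tabulates DLTs together with treatment delays and dose reductions.

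**The concern.** A percentage of patients with at least one event can only rise as follow-up lengthens. Here follow-up ends 30 days after the last dose, and the last dose depends on progression, toxicity and patient choice. Two dose levels can therefore differ in their AE percentages because one is more toxic, because its patients were watched for longer, or both. The planned tables give no means of telling these apart.

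A most-extreme-value laboratory table has the same property: the longer the observation, the more chances for an extreme value. With 1 to 9 patients per level, one long-treated patient can dominate a row. At stake is how the descriptive tables for the primary endpoint are read across dose levels. The problem arises even if no patient changes dose.

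**Working it through.** The documents give no exposure ratio and no expected AE rate, so there is no figure of the plan's own to reproduce. The windows follow from the schedule; the event risks below are assumptions.

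**1. Window length.** The last dose of full cycle c falls on day 28(c − 1) + 15, and documentation runs 30 days beyond it:

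T(c) = 28(c − 1) + 15 + 30

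| Treatment received | Window (days) |
|---|---|
| Single dose | 1 + 30 = 31 |
| 1 cycle | 0 + 15 + 30 = 45 |
| 2 cycles | 28 + 15 + 30 = 73 |
| 4 cycles | 84 + 15 + 30 = 129 |
| 6 cycles | 140 + 15 + 30 = 185 |
| 12 cycles | 308 + 15 + 30 = 353 |

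Ratios: 6 cycles against 1, 185/45 = 4.1; 6 against 2, 185/73 = 2.5; 6 against a single dose, 185/31 = 6.0; 12 against 1, 353/45 = 7.8. If the last dose in cycle 6 is on day 1, the window is 140 + 1 + 30 = 171 days and the first ratio is 171/45 = 3.8. Cycle 6 is only the last scheduled marrow assessment (section 4), not a limit on treatment.

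**2. When the order reverses.** Assume a constant hazard h at the milder dose and m·h at the more toxic dose. With a risk p per 28 days at the milder dose, h = −ln(1 − p)/28. The percentage with an event by day T is 1 − exp(−hT) at the milder dose and 1 − exp(−m·h·T) at the more toxic dose. The more toxic dose shows the lower percentage exactly when m is smaller than the window ratio T(milder)/T(more toxic).

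**3. Size.** Milder dose given for 6 cycles, p = 10%: 1 − 0.9^(185/28) = 50%.

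| Hazard multiple m | More toxic dose left after 1 cycle | Left after 2 cycles |
|---|---|---|
| 2 | 29% (reversed) | 42% (reversed) |
| 3 | 40% (reversed) | 56% (correct order) |
| 4 | 49% (reversed, barely) | 67% (correct order) |
| 5 | 57% (correct order) | 75% (correct order) |

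For m = 2 and one cycle at the more toxic dose, p = 5% gives 15% against 29%, and p = 20% gives 51% against 77%.

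**4. Sensitivity to duration.** Take risks of 40% and 20% per 28 days, so m = ln(0.6)/ln(0.8) = 2.3. If the more toxic dose is left after 2 cycles it shows 1 − 0.6^(73/28) = 74%. The milder dose shows 1 − 0.8^(185/28) = 77% after 6 cycles, which is almost no difference, and 1 − 0.8^(129/28) = 64% after 4 cycles, which is the correct order.

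**5. Cohorts of the planned size.** With p = 10%, m = 2, and one cycle against six, exact binomial sums give the chance that the more toxic dose shows the strictly lower observed percentage. In a common 28-day window the true risks are 19% (1 − 0.9²) and 10%.

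| Patients per level | Whole window | 28-day window |
|---|---|---|
| 9 and 9 | 0.76 | 0.18 |
| 3 and 3 | 0.56 | 0.15 |

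**6. Front-loaded risk.** If all risk lies in the first 28 days, even the shortest planned window (31 days) covers it. The whole-window percentages are then 19% and 10%, and the bias disappears.

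**The case against.** - **The dose decision rests on a common window.** This stands. DLTs are counted in cycle 1 for every patient, they drive escalation and the MTD, and section 13.3 tabulates them. A reader might infer that no safety table uses a common window, or that the trial's main dose conclusion is confounded with time at risk. The documents support neither. What remains is that the primary endpoint is AEs as a whole, not DLTs alone.
- **A patient who stops for a toxicity is already counted.** True for that event. The tables run by preferred term and organ class, however, and the same patient's time at risk for every other term is cut short. Reversal within one term needs patients to leave for another reason: progression, refusal or a different toxicity.
- **The one-against-six-cycle example is a corner case.** This also stands. The Synopsis places progression assessment after 2 cycles, and step 4 shows that the reversal then nearly vanishes or does not occur. Reversal is possible, not predicted.
- **Events cluster at the infusion.** Section 10.1.8 reports several events during infusion or within 3 hours. That removes the bias only if they are confined to the first infusions. Otherwise risk recurs with each dose: 3 in one cycle, 10 to 18 over six. The same section also lists delayed and late toxicities.
- **Cohorts are tiny and a full SAP will follow.** Sampling noise is large under any method (0.15 to 0.18 in step 5), but it does not excuse a systematic component. The full SAP is the natural place for the change.

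**Conclusion.** The by-dose AE percentages in section 13.2.3, and the optional worst-grade laboratory tables, mix toxicity with time at risk, and nothing planned in section 13 separates them. Windows differ about fourfold between 6 cycles and 1. That figure might be taken as a maximum, but it is not: with no cycle cap, the documents set no upper limit.

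The size of the distortion rests on three assumptions: that the section 11.2 documentation window is the one used in the tables, that event risk persists over time, and that dose levels differ in how long patients stay on treatment. Under these, the order of two doses reverses when the hazard ratio is below the window ratio. If events cluster at the first infusions, the bias shrinks and may vanish.

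DLT counts, escalation and the MTD are untouched. This is a cheap improvement to the descriptive tables for the primary endpoint, not a defect in the dose-finding design.

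**What to change.** In section 13.2.3, or in the full SAP:

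1. State the window that defines treatment-emergent.
2. Add, by assigned dose level, a table of AE incidence (all, related, grade 3 or higher, serious) and worst laboratory grade restricted to the 28 days of cycle 1. Use it for comparisons between dose levels. Even a patient stopped after one infusion has 31 planned days of AE documentation, so the AE window is covered for every treated patient unless the patient dies or is lost. It also ends before within-patient escalation, which is allowed only after 2 cycles.
3. Keep the whole-treatment tables in full. Reducing them to a listing might look like a natural next step, but it would hide late and cumulative toxicity; section 10.1.9 notes that some hepatic effects of methotrexate generally follow prolonged use.
4. Beside the whole-treatment tables, show exposure by dose level and events per patient-month, counted from first dose to last dose plus 30 days.

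The cost is SAP wording and slightly longer output. Section 11.2 already requires the date and grade of every toxicity on internal study forms, so no new data are needed. The limits should be stated: the cycle 1 table does not show late events, and person-time rates are imprecise in cohorts of 1 to 9.
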